Low versus High Dose Tranexamic Acid in Adult Spinal Deformity Surgery: A Randomized, Controlled Trial

NCT 02053363

08/01/2018

Statistical Analysis Plan

Parametric data were expressed as mean \pm standard deviation and compared using the Student t test and Chi-square. Nonparametric data were expressed as median (interquartile range) and compared via the Mann-Whitney U test. Prior to analysis, outlier values were examined to determine their origin and ensure they did not represent data entry errors. Enrollment and surgical data were compared to ensure successful randomization. Data were analyzed on an intention-to-treat basis. Only patients who enrolled and underwent surgery were considered completed. Randomization failures were patients who enrolled but failed to undergo surgery as scheduled and were not randomized. Mean EBL was the primary outcome measure, while number of PRBC transfused, mean number of intraoperative complications and 90-day complications were secondary outcomes. All tests were 2 sided and were considered statistically significant if the P value was less than 0.05. Statistical analysis was performed using JMP, version 13 (SAS Institute Inc., Cary, North Carolina, USA).

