### Research Design and Methods

Study Design: Randomized, double blind, controlled Trial at a single institution. The study will be registered at [www.ClinicalTrials.gov](http://www.ClinicalTrials.gov) .

**Power Analysis:** We anticipated an intraoperative estimated blood loss (EBL) of 2,000mL with a standard deviation of 500mL in the control group. A difference of 400mL was estimated to be a clinically relevant difference, as differences in excess of 400mL may result in additional units of allogeneic packed red blood cell transfusion during and after surgery. A sample size of 26 patients per group (52 total) was needed to find a difference of 400mL with a power of 80% and alpha defined as 0.05. In anticipation of nonadherence and loss to follow up, target enrollment was 60 patients.

**Selection Protocol:** Following Institutional Review Board (IRB) approval, adult patients (ages 18-75) scheduled to undergo long segment (Upper Instrumented Vertebra (UIV) T5 or proximal and Lower Instrumented Vertebra (LIV) L3 or distal) posterior spinal fusion with instrumentation (PSF) for adult scoliosis without a current deep venous thrombosis (DVT), TXA related contraindications, or other distinct contraindications are eligible and consent for participation will be sought.

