#### Contraindications to Enrollment

1. Any patient who pre-donates autologous blood for intra- or postoperative use. (Directed donor units are acceptable).
2. Any patient with history of suspected blood disorders or abnormal coagulation laboratory results.
3. Any patient on anticoagulation therapy that cannot be interrupted.
4. Any patient with history of deep vein thrombosis (DVT).
5. Any patient with impaired renal function or serum creatinine > 1.5.

All eligible patients will be provided with a detailed explanation of the study as well as a copy of an Investigational Review Board (IRB) approved informed consent form to take home and review. Only after all patient questions have been answered and the patient is agreeable to participation, will an informed consent be obtained. A study coordinator will obtain and complete baseline data forms.

**Patient Randomization:** After consent is obtained and the patient is enrolled in the trial, patients will be assigned deidentified, unique ID numbers. Randomization of these IDs to either low or high dose tranexamic acid will occur via a computer generated random assignment. Given the variations that may exist in surgical technique (e.g. performance of osteotomies), stratified randomization will be performed by attending surgeon. Based upon the randomization, the pharmacy will prepare tranexamic acid (TXA) for one of two intravenous dosing protocols(independent variable): (1) Low Dose(Standard of Care/Control): Loading Dose 10mg/kg given over 15 minutes, followed by 1mg/kg/hr via continuous infusion (2) High Dose(Study Group): Loading Dose 100mg/kg given over 15 minutes, followed by

10mg/kg/hr via continuous infusion. The medications will be delivered to the operating room in identical packaging for both treatment groups, and labeled "TXA Study Drug." All patients will receive a test dose prior to the induction of general anesthesia. The surgeon, anesthesia team, and operating room staff will be blind to the concentration of TXA in the medications received. Treatments may be "unblinded" at the discretion of the surgeon and anesthesiologist, in cases of extreme blood loss. If additional anti-fibrinolytics are given, the change in dose will be recorded. The loading dose will be given to coincide with incision. The continuous infusion will be stopped at the conclusion of fascial layer closure.

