**Surgical Technique:** A standard, midline, subperiosteal approach will be taken to the spine. Hemostasis will be achieved with electrocautery. Mean arterial pressures (MAP) will be maintained between 60-80mmHg in an effort to minimize blood loss. At the discretion of the surgeon, posterior column osteotomies and three column osteotomies/vertebral column resections will be performed. When performed, the number and location will be recorded. Pedicle screw instrumentation will be used preferentially. Extension to the ilium will accompany any lumbosacral fusion. Standard reduction techniques will be used. The dorsal elements will be decorticated, as a last measure. Iliac crest will not be harvested, unless specifically requested by the patient, or if a contraindication to the use of bone morphogenetic protein-2 (rhBMP-2) exists. Intraoperative red blood cell salvage will be used. Subfascial and suprafascial drains will be placed routinely. All wounds will be closed routinely, in layers. Drains will be removed on postoperative day #3 or when output is 30cc or less over an 8 hour shift.

**Postoperative Protocol:** All patients are mobilized on postoperative day #1. Complete blood counts (CBC) are obtained on postoperative days #1-3. A transfusion trigger for all patients will exist at a Hemoglobin level of 8.0 g/dL. Patients with a higher hemoglobin level, with symptomatic anemia, who are refractory to fluid repletion will receive allogeneic red cell transfusions. All patients are kept nothing by mouth until a return of bowel function. Until diets are advanced, patients will receive intravenous maintenance fluids. All patients receive respiratory therapy postoperatively, to include incentive spirometry and intermittent positive pressure breathing.

**Data Collection:** Routine demographic data will be collected at enrollment:

1. Age
2. Weight (kg)
3. Height (cm)
4. Gender
5. Race
6. Primary Diagnosis
7. Standard Scoliosis Research Society Radiographic Measurements
  - a. Coronal / Sagittal Cobb Measurements
  - b. Coronal / Sagittal Alignment by C7 Plumb Lines
8. Charlson Comorbidity Index
9. American Society of Anesthesiologists' (ASA) Score
10. Nicotine Status

11. Complete Blood Count
12. Coagulation Profile (PT/PTT/INR)
13. Narcotic Use (None / Mild Narcotic / Strong Narcotic / Quantities)
14. Allergies
15. Preoperative Neurologic Exam
16. Scoliosis Research Society – 22 Score
17. Oswestry Disability Index Score

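### Randomisation is stratified by attending surgeon, but the planned EBL comparison has no surgeon term, which gives up precision if surgeon affects blood loss

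*SAP*

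**What the plan says.** Under Patient Randomization, the protocol states: "Given the variations that may exist in surgical technique (e.g. performance of osteotomies), stratified randomization will be performed by attending surgeon". The mechanism is described only as an allocation that "will occur via a computer generated random assignment". No block size or number of surgeons is given. Under Surgical Technique it adds: "At the discretion of the surgeon, posterior column osteotomies and three column osteotomies/vertebral column resections will be performed".

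The Power Analysis is an unadjusted two-group calculation on intraoperative EBL, with a control mean of 2,000 mL, SD 500 mL, 80% power and alpha 0.05: "A sample size of 26 patients per group (52 total) was needed to find a difference of 400mL". Target enrolment is 60.

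The SAP is a single paragraph. Mean EBL is the primary outcome. Parametric data are "compared using the Student t test and Chi-square" and nonparametric data are "compared via the Mann-Whitney U test". It names no covariate, regression or stratified test and does not mention surgeon. The protocol has no analysis section that fills the gap.

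**The concern.** The design treats surgeon as a likely source of variation in blood loss, and the analysis ignores it. A pooled two-sample test leaves any between-surgeon variation in the error term. The consequence depends on how the allocation list was built, which the documents do not say.

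- **Balanced within surgeon (for example, permuted blocks).** Between-surgeon variation largely drops out of the true sampling error of the arm difference, but the t test still counts it. If surgeon affects EBL, the reported standard error and CI are too wide and the test's size is below 5%.
- **Not balanced within surgeon.** Stratifying without blocks gives no more balance than simple randomisation. The t test is then correctly calibrated but less efficient than an adjusted analysis.
- **No surgeon effect on EBL.** Nothing is gained by adjusting.

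The trial is small, and its unadjusted CI half-width of about 279 mL is already a large part of the 400 mL difference it is designed to detect. An avoidable loss of precision therefore deserves attention.

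**Working it through.** **Inputs from the documents.** Difference 400 mL, SD 500 mL, two-sided alpha 0.05, 26 per group (N = 52).

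**Assumed, because the documents are silent.** The share of EBL variance due to surgeon (R²) is 0, 10, 20 or 30%. There are three surgeons of near-equal volume (18/17/17). Allocation is either in blocks of 4 within surgeon or by simple randomisation. Total SD is held at 500 mL.

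**Step 1: the plan's own figure.** SE = 500 × √(2/26) = 138.7 mL, so the noncentrality is 400/138.7 = 2.88. Exact noncentral-t power on 50 df is 80.7% at 26 per group and 79.2% at 25. The stated 26 per group is reproduced, for an unadjusted t test.

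**Step 2: precision with surgeon in the model, arms balanced within surgeon.** Residual SD = 500 × √(1 − R²). CI half-width = t(0.975) × residual SD × √(2/26), with 50 df unadjusted and 48 df adjusted for three surgeons. Power is from the noncentral t on 48 df.

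| R² | Residual SD (mL) | True SE (mL) | 95% CI half-width (mL) | Power, adjusted |
|---|---|---|---|---|
| 0 (unadjusted) | 500.0 | 138.7 | 2.009 × 138.7 = 279 | 80.7% |
| 10% | 474.3 | 131.6 | 2.011 × 131.6 = 265 | 84.6% |
| 20% | 447.2 | 124.0 | 2.011 × 124.0 = 249 | 88.5% |
| 30% | 418.3 | 116.0 | 2.011 × 116.0 = 233 | 92.2% |

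**Step 3: size of the t test under balance.** The t test goes on estimating an SE near 138.7 mL whatever R² is. At R² = 20% its statistic is therefore shrunk by about 124.0/138.7 = 0.894. The nominal critical value of 2.009 acts like 2.009/0.894 = 2.25, which corresponds to a two-sided size of about 3%.

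**Step 4: simulation.** 10,000 trials per setting, comparing the pooled t test with least squares including surgeon indicators. Monte Carlo error is about 0.2 points for size and 0.4 for power.

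| Allocation | Quantity | R² = 0 | 10% | 20% | 30% |
|---|---|---|---|---|---|
| Blocks of 4 | t-test size | 4.9% | 4.2% | 3.1% | 2.1% |
| Blocks of 4 | True SE of the difference (t test reports 138–139 mL) | 139 | 132 | 125 | 117 |
| Blocks of 4 | Power, unadjusted / adjusted | 80 / 80 | 82 / 85 | 83 / 88 | 85 / 92 |
| Simple | Power, unadjusted / adjusted | 80 / 78 | 79 / 82 | 80 / 87 | 80 / 91 |

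Under simple randomisation the t test's size stays at 4.7–5.1%, and its reported SE (139–140 mL) matches the true one (140–141 mL). At R² = 20%, the chance of missing a true 400 mL difference falls from 100 − 83 = 17% to 100 − 88 = 12% with blocking, and from 100 − 80 = 20% to 100 − 87 = 13% without.

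**Step 5: sensitivity to the number of surgeons.** With 2, 3 or 5 equal surgeons, or three unequal ones (30/16/6), the gain at 10/20/30% is 2–3/5–6/8 points with blocking and 1–4/5–7/10–12 without. At 0% the gain is nil with blocking, and there is a cost of 1–3 points without.

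A separate simulation of 20,000 trials per setting, with arms exactly balanced within surgeon, agrees. At R² = 20%, t-test size is 2.8% and power 82.7% against 88.2%. With arms not balanced within surgeon, power is 80.0% against 87.2%.

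The secondary outcomes were not examined.

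**The case against.** The strongest reply is that nothing here is invalid. The trial was sized for an unadjusted comparison and runs one. That comparison is unbiased, holds its error rate and delivers the planned power. This is correct, and it limits the point to forgone precision.

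The size of a surgeon effect is also unknown. The protocol says only that variations may exist. It describes a single institution and standardises much of the operation, including approach, haemostasis, blood-pressure range and cell salvage. Osteotomies at the surgeon's discretion may be decided patient by patient, which a surgeon indicator would not capture. At R² = 5% the gain is small: 81.3% to 82.6% with blocks of 4, and 79.6% to 79.9% with simple randomisation. If all 60 enrolled patients were analysed (20/20/20), power at 20% would rise from 88.7% to 92.7% blocked, or from 85.9% to 91.4% unblocked. These are smaller gains from a start already above plan. All of this stands as a limit on magnitude, and it is why the full range should be read rather than the 20% case alone. It does not remove the mismatch: the protocol judged surgeon important enough to stratify on, and the cost of adjusting is small even if that judgement was wrong.

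Finally, the SAP is dated 08/01/2018 and written in the past tense. If outcomes had already been analysed, changing the primary test would be a post hoc choice. That also stands, and it determines the form of the fix.

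**Conclusion.** The point holds as a loss of precision, conditional on surgeon affecting EBL. It is not a validity error, and the sample size is not undermined. Under the assumed surgeon shares of 10–30% and three near-equal surgeons, omitting surgeon costs about 3–8 points of power if allocation was blocked within surgeon and about 3–11 if it was not. With balance within surgeon, the CI half-width is also about 14–46 mL wider than it need be (279 − 265 to 279 − 233). If surgeon has no effect, the omission costs nothing under blocking and saves 1–3 points without it. The documents cannot place the trial within this range, because they give no surgeon variance share, number of surgeons or block size. The change should be made, with moderate confidence in how much it gains.

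**What to change.** - **Primary analysis.** Fit a linear model of intraoperative EBL (the outcome used in the Power Analysis) on treatment arm and attending surgeon. Report the adjusted mean difference in mL with its 95% CI.
- **Small strata.** Pool surgeons with fewer than a pre-set number of patients (for example, 4) into one stratum, by a rule fixed without sight of outcomes.
- **Rank route.** If EBL is treated as nonparametric, replace Mann-Whitney with a surgeon-stratified rank test (van Elteren). The gain from this test and from the pooling rule was not simulated.
- **Sensitivity analysis.** Keep the unadjusted t test.
- **Disclosure.** State whether allocation was blocked within surgeon and the block size.
- **Timing.** If outcome data had already been analysed when the change is made, leave the t test as the primary analysis. Show the surgeon-adjusted result beside it, labelled as added afterwards.

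The cost is SAP wording and one covariate that randomisation already required, with no extra patients or data. The model uses one degree of freedom fewer than the number of surgeon strata after pooling. If surgeon has no effect and allocation was not blocked, about 1–3 points of power are lost.

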18. Visual Analog Pain Score

Intraoperative data collected will include:

1. Procedure Length (Incision to Skin Closure, minutes)
2. Levels Fused
3. Levels of Instrumentation and Type
4. Osteotomies Performed (Yes / No / Type)
5. Hemoglobin Concentration at Incision, Closure (by Arterial Blood Gas)
6. Estimated Blood Loss (estimated as three times cell saver volume)
7. Crystalloid / Colloid Volume Infused
8. Allogeneic Packed, Red Blood Cells (PRBC) / Fresh Frozen Plasma (FFP) / Platelets (PLT) Transfused
9. Urine Output
10. Intraoperative Surgical Complications

Postoperative data collected will include:

1. Drain Output (with Length of Drain Use)
2. CBC on Postoperative Days #1,2, and 3
3. Units of PRBC / FFP / PLT Transfused
4. Length of Hospital Stay
5. Disposition at Discharge
6. Acute Perioperative Complications
7. Duplex Ultrasound Scan of Lower Extremities Result

Followup visits will be six weeks and three months to capture complications potentially related to TXA at up to three months after surgery. At these visits, SRS-22 and ODI scores will be obtained. The dependent variables of interest are:

1. Intraoperative and Total Estimated Blood Loss
2. Number of PRBC Units Transfused
3. Intraoperative and Acute Complications (up to three months)

All findings will be reported using CONSORT guidelines.

Human Subjects

All protocol violations will be reported to the Washington University IRB. All serious adverse events (SAE's) will be reported to the Washington University IRB within 15 days of occurrence. SAE will be tracked and potential association with TXA administration will be determined site PI. Any frequently occurring SAE felt to be associated with TXA administration will be reported to all participating centers as well as Med Watch.

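### Does the SAP need to define total estimated blood loss, label its primary outcome as intraoperative, and plan a confidence interval?

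*SAP*

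**What the plan says.** The SAP's outcome sentence reads: "Mean EBL was the primary outcome measure, while number of PRBC transfused, mean number of intraoperative complications and 90-day complications were secondary outcomes". It reports parametric data as mean and SD with a t test, and nonparametric data as median and interquartile range with a Mann-Whitney test. It mentions no confidence interval.

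The protocol bears on blood loss in four places:

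- **Power Analysis:** "We anticipated an intraoperative estimated blood loss (EBL) of 2,000mL with a standard deviation of 500mL in the control group". The 400 mL target is justified because "differences in excess of 400mL may result in additional units of allogeneic packed red blood cell transfusion during and after surgery".
- **Data Collection, intraoperative list:** the only formula for blood loss, "Estimated Blood Loss (estimated as three times cell saver volume".
- **Data Collection, postoperative list:** "Drain Output (with Length of Drain Use", with no stated link to any blood loss total. Under Surgical Technique, "Subfascial and suprafascial drains will be placed routinely" and "Drains will be removed on postoperative day #3 or when output is 30cc or less over an 8 hour shift".
- **Data Collection, dependent variables:** the first item is "Intraoperative and Total Estimated Blood Loss".

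The protocol therefore names two blood loss outcomes and the SAP names one.

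**The concern.** Three things look wrong on a first reading.

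1. Total blood loss is part of the first dependent variable in the protocol. It is missing from the SAP without a statement that it was dropped, and it has no formula or time window. Two analysts could count drain output differently and both claim to follow the protocol.
2. The SAP's EBL is unqualified. If it could mean total loss, the stated power might not belong to the primary outcome.
3. A P value alone does not tell the reader whether a 400 mL benefit has been ruled out. With about 26 to 30 patients per arm, that question could well arise.

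At stake would be a blood loss figure defined after the fact, and a non-significant primary result that is hard to interpret.

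**Working it through.** **Step 1. Which blood loss is primary?** Inputs from the Power Analysis: difference 400 mL, SD 500 mL, power 80%, alpha 0.05. The SAP makes tests two-sided.

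Normal approximation: n per group = 2 × (1.960 + 0.842)² × 500² / 400² = 2 × 7.85 × 1.5625 = 24.5, rounded up to 25.

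Noncentral t: power is 79.1% at 25 per group and 80.7% at 26. The plan's 26 is therefore the exact two-sample t test answer. A one-sided test would need 20 by the normal approximation, which does not match.

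The calculation is explicitly for intraoperative loss, and that is where the abbreviation EBL is introduced. The only formula is in the intraoperative list, and the SAP speaks of a mean. All of this points to one reading: mean intraoperative EBL, compared by t test.

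The other reading would matter if anything supported it. The documents give no SD for total loss. If it were 600, 700, 800 or 1,000 mL (assumptions) with the difference still 400 mL, power at 26 per group would be 65%, 52%, 42% or 29%. Nothing in either document points that way.

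**Step 2. Is the confidence interval lost?** Half-width = t(0.975, 2n − 2) × SD × √(2/n).

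| n per group | t | 500 × √(2/n) | Half-width |
|---|---|---|---|
| 26 | 2.009 | 138.7 | 279 mL |
| 30 | 2.002 | 129.1 | 258 mL |

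At 26 per group, an observed reduction between 400 − 279 = 121 mL and 279 mL would be non-significant with 400 mL still inside the interval. At 30 per group the range is 142 to 258 mL. Such a result is possible, but its probability is set by the sample size and is the same whether or not the interval is printed. The interval needs only the two means, the two SDs and the group sizes, and the SAP already plans to report means with SDs.

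Rebuilding it would fail only if the primary were reported as medians. If EBL were log-normal with the plan's mean of 2,000 mL and SD of 500 mL, a 400 mL difference in means corresponds to a median difference of 388 mL (constant coefficient of variation) or 413 mL (equal SDs). That is a shift of 12 to 13 mL, which is immaterial.

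**Step 3. Is total loss really undefinable?** The protocol lists drain output together with how long the drains were in place. It does not list output by shift, by day or by drain site. A cumulative volume to removal is thus the one postoperative quantity that the listed data clearly support, and intraoperative loss plus that volume is the natural total. A 24-hour window or a by-site total may not be computable from the listed data, so the analyst has less freedom than first appears.

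How much drainage could add cannot be settled from the documents. As an illustration under assumed inputs (two drains, first-shift output averaging 75 to 150 mL per drain, half-life 16 to 36 hours, removal threshold applied to each drain), mean drainage to removal is about 377 to 1,629 mL. A further assumed 25% reduction with high dose would widen the difference between arms by 127 to 483 mL; with no dose effect on drainage it would not widen. These figures show that the definition affects a reported total. They do not touch the primary.

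**Step 4. What would listing total loss as a secondary do?** The SAP has three secondaries and no multiplicity adjustment. If they were independent, the chance of at least one false positive would go from 1 − 0.95³ = 14.3% to 1 − 0.95⁴ = 18.5%. The primary test would not change.

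**The case for a change.** The strongest case for a change is that an outcome listed in the protocol has vanished from the SAP without a word, and one sentence would settle it. The Power Analysis also appeals to transfusion after surgery, yet postoperative loss is recorded and has no named place among the outcomes. Because the SAP is dated 08/01/2018 and written in the past tense, a total reported later could rest on a definition chosen after the data were seen.

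Part of this stands. The two documents do differ, and neither says why. Anyone reporting total loss should state how it was built and should not present it as a fully prespecified outcome.

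The rest is weaker. The 400 mL argument concerns a difference in intraoperative loss that may lead to later transfusion; it does not call for postoperative loss to be analysed. Its stated consequence, red cell transfusion, is collected during and after surgery and is kept as an SAP secondary. The SAP's general rules for summarising and comparing data can be applied to drain output, even though it is not a named outcome. On timing, if the data had already been seen when the SAP was written, adding a definition now would not make it prespecified.

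**Conclusion.** No change to the plan follows. The discrepancy over total blood loss is genuine, but it is a missing detail in an outcome that the SAP does not test, and an analyst can fill it sensibly with the data the protocol lists. The primary is clear enough: mean intraoperative EBL, for which the stated 26 per group reproduces with 80.7% power. Adding the word intraoperative would be editorial. A printed confidence interval is good reporting practice, but it changes no result and can be rebuilt from the planned summaries (half-width 279 mL at 26 per group, 258 mL at 30, assuming the plan's SD of 500 mL).

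This rests on two readings: that EBL in the SAP means what the Power Analysis means by it, and that the primary is reported as means with SDs. Sample size, power and type I error for the primary are unaffected under both. The drainage figures and the SDs for total loss are assumptions and carry no weight in the conclusion. A sentence reconciling the two documents would be a harmless courtesy to the reader.

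### PRBC units depend partly on starting haemoglobin, yet the SAP compares them unadjusted: a modest, avoidable loss of precision on a secondary outcome

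*SAP*

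**What the plan says.** The SAP names mean EBL as primary, "while number of PRBC transfused, mean number of intraoperative complications and 90-day complications were secondary outcomes". It lists the Student t test, Chi-square and the Mann-Whitney U test, two-sided at 0.05, and no model with covariates. Enrolment data appear only in a comparison meant to confirm that randomisation worked.

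The Protocol supplies the rest:

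- **Postoperative Protocol:** "A transfusion trigger for all patients will exist at a Hemoglobin level of 8.0 g/dL". The next sentence widens the rule: "Patients with a higher hemoglobin level, with symptomatic anemia, who are refractory to fluid repletion will receive allogeneic red cell transfusions".
- **Data Collection, enrolment list:** "Routine demographic data will be collected at enrollment"; item 11 is "Complete Blood Count". Haemoglobin at incision and at closure is recorded later, during surgery.
- **Data Collection, transfusion:** red cells are recorded in both periods, as "Allogeneic Packed, Red Blood Cells (PRBC) / Fresh Frozen Plasma (FFP) / Platelets (PLT) Transfused" during surgery and "Units of PRBC / FFP / PLT Transfused" afterwards. No trigger is stated for intraoperative transfusion.
- **Patient Randomization:** stratified by attending surgeon only.

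Neither document gives an SD, an expected difference, a power figure or a correlation with haemoglobin for PRBC units.

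**The concern.** Under a threshold rule, whether a patient is transfused depends on starting haemoglobin minus the fall. Tranexamic acid can act only on the fall. Two patients with equal blood loss can therefore receive different numbers of units because they started at different levels. That variation has nothing to do with treatment, is fixed before randomisation and is already measured, but the planned tests leave it in the error term.

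Units are the only efficacy outcome among the SAP's secondaries. They are also the Protocol's reason for calling 400 mL clinically relevant (Power Analysis). The trial is sized for EBL, not for units, so precision on units is likely to be short. There is also a practical gap. If the balance check shows a difference in starting haemoglobin, the SAP has no rule for using it, and any adjustment would be chosen after seeing the data.

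**Working it through.** **1. The plan's own figure.** For EBL, with SD 500 mL, difference 400 mL, two-sided 0.05 and 80% power: n per arm = 2 × (1.960 + 0.842)² × (500/400)² = 24.5, so 25. The t-test version gives 25.5, so 26, with power 80.7%. The stated 26 per group reproduces, and 52/60 implies 13.3% attrition. Nothing below alters this. There is no corresponding figure for units to reproduce.

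**2. Chance imbalance.** The SD of the difference in mean starting haemoglobin is SD × √(2/n). At 30 per arm √(2/30) = 0.258, so an assumed SD of 1.0–1.4 g/dL gives 0.26–0.36 g/dL. A gap above 0.5 SD occurs with probability 5.3% at 30 per arm and 7.1% at 26.

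**3. What adjustment can give.** If haemoglobin correlates r with units, the residual variance is multiplied by (1 − r²), so relative efficiency is 1/(1 − r²). With r unknown:

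| r | Relative efficiency | Power at 26 per arm, effect 0.5 SD (42% unadjusted) |
|---|---|---|
| 0.2 | 1.04 | 44% |
| 0.4 | 1.19 | 49% |
| 0.5 | 1.33 | 53% |
| 0.7 | 1.96 | 70% |

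**4. Simulation, trigger only.** All inputs except the 8.0 trigger are assumptions: 30 per arm; start mean 13.0 g/dL, SD 1.0–1.4; fall mean 7.0, SD 1.5–2.0; one unit per 1 g/dL (or part) below 8.0; high dose reduces the fall by 0.8 g/dL (400 mL of an assumed 4.9 L blood volume at 10 g/dL: 400/4,900 × 10 ≈ 0.8, ignoring salvage). The control mean is then 2.6–2.7 units and the true difference about 0.65–0.70.

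| Start SD | Fall SD | Power, t test | Power, adjusted (HC3) |
|---|---|---|---|
| 1.0 | 1.5 | 36% | 46% |
| 1.4 | 1.5 | 31% | 45% |
| 1.0 | 2.0 | 25% | 28% |
| 1.4 | 2.0 | 23% | 28% |

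Starting haemoglobin explains 19–43% of within-arm variance. The formula 1 − √(1 − R²) then gives a standard-error reduction of 10–25%; simulation gives about 8–25%. Adjusted type I error is 4–5%. With half the effect (0.4 g/dL) the power gain is at most about 3 points.

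**5. Units outside the trigger.** Adding an assumed Poisson mean of 1.5 units per patient unrelated to haemoglobin, the variance explained drops to 16–32%, the standard-error reduction to about 6–15%, and the power gain to about 0–5 points.

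**6. Fall scaled from the Protocol.** At 0.8 g/dL per 400 mL, the stated 2,000 mL (SD 500) becomes a fall of 4.0 g/dL (SD 1.0). With the trigger alone, power goes from 30% to 35% (start SD 1.0) and from 24% to 30% (1.4), with a control mean of only 0.3–0.5 units. With 1.5 outside units added, power is below 10% either way and there is no gain.

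**7. Validity of the planned test.** In a separate simulation at 26 per arm (start mean 11.5, SD 0.7–1.5, fall 2 g/dL per litre, 0–1.5 outside units), unadjusted type I error was 4.1–5.7% by t test or Mann-Whitney. With a 400 mL effect, power was 18–54% unadjusted and 23–66% adjusted.

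**The case against.** The strongest reply is that nothing is wrong with the planned comparison. Under randomisation, chance imbalance in haemoglobin is ordinary sampling error, already counted in the standard error and the p-value. That stands. A reader might infer that the unadjusted test is biased or invalid; neither the design nor the simulations support that.

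A reader might also infer that the trigger governs PRBC units and that starting haemoglobin determines them strongly. The documents do not go that far. The trigger sits in the postoperative section, the next sentence permits transfusion above it, and intraoperative units enter the outcome with no stated trigger. Cell salvage is also used (Surgical Technique). This too stands, and steps 5 and 6 show how much it can shrink the benefit.

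The assumed 7.0 g/dL fall corresponds, at the same conversion, to about 3.5 L, well above the Protocol's 2,000 mL intraoperative figure. Postoperative loss could fill the gap, but no figure in the documents says so. The larger gains are therefore the favourable end of the range.

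Finally, the SAP is dated 08/01/2018 and written in the past tense. If the analysis has been done, a covariate added now is not prespecified.

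What survives is narrower: a pre-treatment variable with a plausible link to the outcome is collected and left out of the comparison, and including it costs little.

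**Conclusion.** The point holds as an efficiency improvement on one secondary outcome, not as an error. Units depend partly on starting haemoglobin, the SAP leaves that out, and the cost is precision only.

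The size rests on assumed distributions. The 8–25% reduction in standard error requires that the trigger alone drives transfusion; about 6–15% is the figure with 1.5 outside units under the same assumed fall. With a fall scaled from the Protocol's EBL and outside units added, the gain in power vanishes. In every 30-per-arm setting examined, adjusted power for units stays below 50%, so adjustment would not turn this into a well-powered outcome. The direction is reasonably secure; the size is not.

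**What to change.** State in the SAP that total PRBC units (intraoperative plus postoperative) will be compared by linear regression on arm, enrolment haemoglobin and attending surgeon, with HC3 standard errors. Report the adjusted difference in units with its 95% CI, and keep the unadjusted comparison as supporting.

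- **Why enrolment haemoglobin:** it precedes randomisation. The value at incision coincides with the loading dose and follows the test dose. The price is that an enrolment value may be some time before surgery; the documents do not give the interval.
- **Why surgeon:** it is the stratification factor. The simulations did not include it. Fix in advance how surgeons with very few patients are pooled, because HC3 is undefined for a patient who is the only one in a category.
- **Why one linear model:** it gives a difference in units directly, whereas a log-link count model gives a ratio. Naming a single model leaves no choice open.

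If outcome data have already been analysed, report the adjusted analysis but label it post hoc.

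The cost is a sentence or two in the SAP and no new data or patients. The downside is that a model replaces a simple test for a gain that may be small.
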